### Methods:

TranS-C will be implemented in at least ten counties in California, United States (N = 96 providers; N = 576 clients) via facilitation. CMHC sites are cluster-randomized by county to Adapted TranS-C or Standard TranS-C. Then, within each county, patients are randomized to immediate TranS-C or usual care followed by delayed treatment with TranS-C (UC-DT). Aim 1 will compare TranS-C (combined Adapted and Standard) with UC-DT on improvements in sleep and circadian problems, functional impairment, and psychiatric symptoms. Sleep and circadian problems will also be tested as a mediator between treatment condition (combined TranS-C versus UC-DT) and functional impairment/psychiatric symptoms. Aim 2 will evaluate whether Adapted TranS-C is superior to Standard TranS-C with respect to provider perceptions of fit. Aim 3 will evaluate whether the relation between TranS-C treatment condition (Adapted versus Standard) and patient outcomes is mediated by better provider perceptions of fit in the Adapted condition. Exploratory analyses will: (1) compare Adapted versus Standard TranS-C on patient perceptions of credibility/improvement and select PhenX Toolkit outcomes; and (2) evaluate possible moderators.

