### 3.3 Recruitment

#### 3.3.1 Community Mental Health Centers

Building the CMHC network that forms the basis for this study began in August 2013 with outreach by the PI. The network has been maintained via newsletters, meetings, and workshops on EBPTs. Originally, eight counties agreed to participate. At various stages of the study, we have continued to focus on recruiting new counties and new CMHC sites to maximize provider and patient sample size goals. Most counties consist of three to 10 CMHC sites. Sites in the following ten counties in California, United States are currently participating in the Implementation Phase: Alameda, Contra Costa, Kings, Monterey, Placer, Santa Cruz, Solano, Santa Clara, Santa Barbara, and Lake. Note that sites in San Luis Obispo are also participating but are operating as part of Monterey County.

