### 3.8 Sample Size

Sample size was determined via power analyses with Optimal Design [85, 86] and Stata 15 [87] and a two-sided alpha of 0.05. We used the original  $N = 8$  counties that agreed to participate, though as noted above, new counties have since been recruited to meet sample size goals determined by the following calculations. For Aims 1 and 3, 60 patients from eight randomized clusters/CMHCs was found to provide over 90% power to detect large effects (average  $d=0.89$  from [35]) between TranS-C and UC-DT, and over 80% power to detect a medium effect ( $d=0.50$ ) between Standard and Adapted TranS-C. For Aim 2, based on a prior study with a similar aim/measure [88], we expected a large effect size ( $d=0.80$ ) between Standard and Adapted TranS-C on the primary outcome of acceptability. Prior studies have reported high correlation coefficients between acceptability, feasibility, and appropriateness ( $rs=.67-.90$ ) [75, 89], thus the analysis for acceptability was expected to sufficiently power the other outcomes. Based on the site intra-class correlation (ICC) estimated from similar prior studies [90, 91], we assumed the ICC to be 0.01 and the inflation factor was calculated as  $1+(n-1)\times ICC$ . Eight clusters with an average cluster size of 10 was found to be needed to achieve over 80% power to detect a large effect for the outcome (acceptability) at the provider level. Thus, to test this aim, we would need at least 80 CMHC providers: 10 providers from 8 CMHCs (at least 4 CMHCs per randomized arm).

In sum, we aimed to randomize at least eight CMHC clinics to either Standard or Adapted TranS-C, with at least 80 providers (10 per CMHC). The goal for patients is 240 patients (30 per CMHC) randomized to immediate Standard or Adapted TranS-C and 240 randomized to UC-DT (30 per CMHC). Adding 20% to account for attrition, the total target sample size for providers is 96 and for patients is 576.

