## 4 PLANNED ANALYSES

### 4.1 Preliminary Analyses and Missing Data

Analyses will use all available data (intent-to-treat) [93]. If dropout is related to other variables, they will be included as predictors. Baseline between-group differences on demographic variables will be examined. These tests will not be used to select covariates in the primary intention-to-treat analysis [94-97]. Instead, covariates will be carefully selected at the conclusion of the trial—given the variations due to COVID-19 and the CMHC context (see Discussion)—and the potential influences of baseline differences will be evaluated as moderators (approach to moderation described below). Analyses comparing TranS-C to UC-DT will evaluate change in outcomes from pre-treatment to post-treatment. Analyses comparing Adapted to Standard TranS-C will evaluate change in outcomes from pre-treatment to post-treatment and pre-treatment to 6FU (see Method and Discussion for more details).

Distributions will be evaluated to detect outliers, and we will ensure that assumptions of planned analyses are met. Covariates will include the patient variables for which we stratified (i.e., age and presence of psychosis or substance use). For all statistical models, counties will be entered as dummy variables rather than a level of analysis due to the relatively small number of clusters. The average intraclass correlation on provider and patient level outcomes will be reported. The Benjamini–Hochberg procedure [98] will be used to correct for multiple testing for confirmatory analyses on the primary outcomes (i.e., sleep disturbance and acceptability) [99].

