### 4.2 Dropout

The N by stage of dropout will be reported for the following: dropout after randomization but before the first treatment session, dropout after treatment has begun but attended half or fewer of the intended number of sessions (i.e.,  $\leq 2$  in Adapted,  $\leq 4$  in Standard), dropout after attended more than half the intended number of sessions (i.e.,  $> 2$  in Adapted,  $> 4$  in Standard) but before treatment has been completed, and dropout after treatment has been completed but prior to post-treatment or 6FU assessments. The number of patients who completed a post-treatment assessment but were lost to 6FU will also be reported. When available, the reasons for dropout and improvement among patients who drop out will be reported.

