First, we did not collect data from leadership at our partner CMHCs. The primary reason was that these leaders have many demands on their time and already had generously collaborated with us on the design and implementation of the study. However, we recognize that leadership-level factors can meaningfully impact implementation outcomes [109]. Thus, exploring leadership perspectives on TranS-C will be an important direction for future research. Second, we considered additional assessment methods for sleep and circadian problems, such as a diagnostic interview (e.g., the Duke Structured Interview for Sleep Disorders; [63]) and polysomnography. However, even without these more intensive diagnostic tools, some patients reported difficulty with the length of assessments. Additionally, we were interested in recruiting patients with a broad range of symptom severity, which may have more ecological validity than a more restricted sample. That said, we acknowledge that there are certain outcomes that we will not be able to address due to this design choice (e.g., change in diagnostic status). Third, assessors are not blind to treatment condition at pre-treatment. To minimize burden on participants (e.g., reduce number of calls from team), assessors are in charge of the consent process, and therefore, they need to provide study-related information—such as number of assessments and treatment sessions—to the patients. At post-treatment and 6FU, we endeavor to keep the assessors blind but, as is common in clinical trials, there are ways that assessors may be able to infer treatment condition (e.g., slightly different assessment batteries). In rare instances, patients in the UC-DT condition ask assessors questions such as “when does treatment start?” or “when will I receive the workbook?” during the post-delay assessment. In such instances, the assessor may be able to ascertain that the patient has been assigned to the UC-DT condition. Assessors receive ongoing supervision and are thoroughly trained to deliver the surveys with integrity and minimal bias. Additionally, relative to interviews or clinical rating scales, the standardized surveys delivered by assessors are likely less vulnerable to bias (see Measures above). However, it is possible that assessor knowledge or hunches about patients’ condition may influence patient responses. Fourth, in the UC-DT condition, patients did not complete a 6FU assessment after the delay. This was a compromise made with CMCH partners, so that patients would not need to wait 7 to 8 months to receive treatment. Thus, analyses comparing TranS-C with UC-DT will evaluate outcomes from pre- to post-treatment, whereas analyses comparing Adapted versus Standard TranS-C can evaluate outcomes from pre- to post-treatment *and* pre- to 6FU. Depending on the outcomes from the trial, an important direction for future research will be testing the long-term effects of TranS-C relative to a control (e.g., UC-DT). Fifth, unforeseen challenges arose related to the COVID-19 pandemic and subsequent mandates in California (e.g., shelter-in-place). For some patients, sleep and circadian treatment became secondary to coping with other mental health ramifications of the pandemic (e.g., anxiety, isolation, grief) or even meeting basic needs of secure access to food and shelter [110]. Additionally, providers suddenly had more demands on their time, such as navigating the shift from in-person to virtual care—a shift that was also challenging for some patients. These changes had implications for the present study. For instance, we did not design the study to systematically evaluate potential differences in TranS-C delivery (i.e., in-person versus virtual versus phone). As another example, there was substantial turnover in providers and patients, leading to more discontinuity across treatment than anticipated. Sixth, some design choices were made to respect the expertise and preferences of our CMHC partners. For example, providers had the option to deliver TranS-C in a group or individual format. Even though this introduced variance into the study, it has been critical to the CMHCs, providers, and patients that we balance rigor with flexibility. We deliberated about whether to control for these variations necessitated by COVID-19 and the CMHC contexts. Ultimately, we decided against a prespecifying a comprehensive list of possible covariates, given the statistical drawbacks of controlling for many variables (e.g., [94-97]). At the conclusion of the trial, the sources of variation that resulted from the COVID-19 pandemic and needs/preferences of our community partners will be carefully considered as to whether they should be included as covariates.

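### Does the 20% attrition add-on leave the provider and patient targets too small?

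*Combined protocol and SAP*

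**What the plan says.** Section 3.8 builds the targets in two steps. For providers, the Aim 2 calculation leads to a minimum: "we would need at least 80 CMHC providers: 10 providers from 8 CMHCs". For patients, "The goal for patients is 240 patients (30 per CMHC) randomized to immediate Standard or Adapted TranS-C", with another 240 assigned to usual care followed by delayed treatment, which makes 480. The allowance for loss comes next: "Adding 20% to account for attrition, the total target sample size for providers is 96 and for patients is 576". The Methods part of the abstract repeats the results as headline sizes ("N = 96 providers; N = 576 clients").

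Neither section 3.8 nor any other section gives an expected attrition rate as a number. Section 3.11 adds some history. The original registration carried a larger sample because a referee of the grant application wanted room for more dropout. The team judged this unfeasible and returned to the size given by the power analysis.

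Three other places bear on the point. Section 3.3.1 lists more counties than the eight used in the calculation: "Sites in the following ten counties in California, United States are currently participating in the Implementation Phase". Section 4.2 commits to reporting patient dropout by stage ("The N by stage of dropout will be reported for the following"). The Discussion, writing of the pandemic period, says that "there was substantial turnover in providers and patients, leading to more discontinuity across treatment than anticipated".

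**The concern.** To keep n participants after a fraction d is lost, one recruits n/(1 − d). Multiplying by (1 + d) gives a smaller number and is a common mistake when d is meant as the loss rate. Here the 20% is tied to attrition, and the totals come from multiplication. A reader who takes 20% as the loss the trial can absorb would be misled in a narrow band. With 17 to 19 providers lost (17.7% to 19.8%) or 97 to 115 patients lost (16.8% to 20.0%), that reader would think 80 and 480 had been kept when they had not.

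The provider figure is stated as a minimum and is linked to power just over 80%, so a shortfall of a few providers could matter in principle. The Discussion's remark on turnover makes it likely that readers will compare the realised loss with the allowance.

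**Working it through.** **Inputs, all from section 3.8 unless noted.** Need before attrition: 80 providers (8 × 10) and 480 patients (240 + 240). Addition: 20%. Two-sided alpha 0.05. Aim 2 effect d = 0.80. Adapted versus Standard effect in patients d = 0.50. ICC 0.01 with inflation factor 1 + (n − 1) × ICC, given for the provider calculation and assumed here for patients as well. Ten counties: section 3.3.1.

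**Step 1: reproduce the plan's totals.**
- Addition: 80 × 1.20 = 96 and 480 × 1.20 = 576. Both match exactly.
- Division: 80/0.80 = 100 and 480/0.80 = 600. Neither matches.

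The wording and the figures therefore agree that the 20% is an addition to the required number.

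**Step 2: what the totals absorb.** (96 − 80)/96 = 16/96 = 16.7%, and (576 − 480)/576 = 96/576 = 16.7%.

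**Step 3: what a 20% loss would leave.** 96 × 0.80 = 76.8, about 77 providers. 576 × 0.80 = 460.8, about 461 patients. The shortfalls are about 3 providers and 19 patients, or 4% of each requirement.

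**Step 4: what that costs in power.** The plan does not print its power formula. As an approximation for sizing only, take a cluster-level t test with J − 2 degrees of freedom and noncentrality d / sqrt[(ICC + (1 − ICC)/n) × (1/a + 1/b)], where n is the number per county and a and b are the counties per arm. With eight counties split 4:4:

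| Comparison | Required number | After 20% loss |
|---|---|---|
| Aim 2, providers, d = 0.80 | 80: 81.3% | 77: 80.0% |
| Adapted vs Standard, immediate arm only, d = 0.50 | 240: 81.0% | 230.4: 79.8% |
| Adapted vs Standard, all 60 patients per cluster, d = 0.50 | 480: 94.8% | 460.8: 94.3% |

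The 81.3% agrees with the plan's claim of over 80% for Aim 2. A normal approximation with the stated inflation factor gives 92.9% to 92.0% for providers and 92.6% to 91.9% for immediate-arm patients. TranS-C versus usual care at d = 0.89 stays above 99.9% on a simple two-group approximation.

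**Step 5: with ten counties.** The same t test reaches 80% power with 68 providers (5:5 split of counties) or 71 (4:6), and with 195 or 204 immediate-arm patients. After a 20% loss, 77 providers and 288 × 0.80 = 230.4 immediate-arm patients remain, more than is needed in every case. Power is then 83.0% to 84.4% for providers and 83.7% to 85.2% for immediate-arm patients.

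These are not the planned models. Section 4.1 says that "counties will be entered as dummy variables rather than a level of analysis", and the tests of interest are treatment-by-time terms. The calculation serves only to show how little a 4% shortfall moves power.

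**The case for a change.** The best argument for a change runs as follows. An allowance made for attrition should say how much attrition it covers, and this one does not. The allowance had already been debated, as section 3.11 shows, so precision was owed. The margin over 80% is thin on the eight-county t test, and the immediate-arm comparison falls just below 80% at a 20% loss. One sentence would cost nothing.

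Part of this stands. The 16.7% is correct, and the expected rate is not given. The rest does not carry a change:

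- The text is not ambiguous between an addition and a loss rate. It describes an addition, and only an addition yields 96 and 576.
- The shortfalls to 77 and 461, and the alternative totals of 100 and 600, need a 20% loss rate that the plan never states.
- The one figure below 80% in the table uses a formula the plan does not print, an ICC the plan does not assign to patients, the immediate arm alone, and eight counties where ten take part.
- Section 4.1 analyses all available data, so the number retained is not a threshold in the analysis. This point should not be pressed far, because a patient with only a pre-treatment record adds little to the estimate of change.
- The Discussion's remark concerns continuity of treatment and gives no rate of missing outcomes. Section 4.2 covers patients, not providers.

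**Conclusion.** The concern does not call for a change. The totals are right for what the plan says it did, and they preserve 80 and 480 up to a 16.7% loss, which any reader can obtain by dividing 80 by 96. The unstated expected rate is a small gap in explanation.

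If the planners did have 20% in mind, the cost would be 4 providers and 24 patients against totals of 100 and 600, and 0.5 to 1.3 percentage points of power for the comparisons tabulated at eight counties. With ten counties the remaining numbers are sufficient on the approximate test. The power figures rest on the inferred t test, an ICC of 0.01 for patients as well as providers, and county splits of 5:5 or 4:6. The 16.7% rests on none of these.

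Recruitment ended in August 2022, before this protocol version of December 2022, so a different inflation rule could not alter enrolment, and no planned analysis depends on it. When results are reported, realised loss can simply be set against 16.7%.

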### 3.9 Data Management and Dissemination

All patient-identifiable data are saved by the assessment team on password-protected fillable PDFs on a secure password-protected and HIPAA-compliant website. On these PDFs, patients and providers are assigned identification numbers. These identification numbers are then used to link anonymized data that is collected via password-protected Qualtrics. When collecting assessments, assessors call participants and enter the data into Qualtrics. Participants also have the option of entering their data directly into a

participant-facing version of the surveys via a HIPAA-compliant version of Qualtrics. Patient-identifiable data is not shared with outside entities during or after the trial. A data management team supervised by the PI, biostatistician (LD), and postdoctoral scholar (LDS) is responsible for downloading, collating, and analyzing the data.

A Data Safety Monitoring Board has been formed to help prevent and manage adverse events. The board includes members with expertise in SMI, psychosocial treatments, and randomized controlled trials. Members are independent from the PI and competing interests. A report was made to the board bi-annually for the first year of the research. Since then, it has shifted to annual reports. However, if safety issues arise, it will be changed to monthly meetings. Yearly reports are submitted to the Committee for the Protection of Human Subjects at UC Berkeley and National Institute of Mental Health.

Outcomes specifically of interest to our partners are presented to CMHC leadership as part of the widely-used implementation strategy, audit and feedback [92]. However, these interim analyses are used only for facilitation purposes. In other words, they do not influence research procedures in any way (e.g., to inform when to terminate the trial).

Results from the trial, as well as analysis code, will be shared via peer-reviewed publications, professional conference presentations, and meetings and newsletters to CMHCs, as relevant. Other than the authors and compliance with data-sharing agreements stipulated by the National Institutes of Health, no other entities have contractual agreements to access the final dataset. Deidentified data are submitted to the National Institute of Mental Health Data Archive twice per year, per their requirements.

### **3.10 Roles and Responsibilities**

This trial is supervised by the PI (AGH), who manages the facilitation team, assessment team, and the data management team. The PI meets with members of each team as needed in addition to daily email communication. Within each team, there is at least one trained lead (ERA, KF, JMS, LD, LDS) who supervises the day-to-day activities of other team members. There is no coordinating center, trial steering committee, or Stakeholder and Public Involvement Group. The responsibilities of each team are detailed elsewhere in this protocol. In summary, the facilitators execute the implementation of TranS-C via numerous activities, including training and supervising CMHC providers in the delivery of TranS-C. The assessment team is responsible for the informed consent process and conducting participant (i.e., provider and patient) evaluations. CMHC leadership and enrolled providers work with the facilitation team to recruit additional providers. CMHC providers help to identify potentially eligible patients, who are then connected with the assessment team for formal eligibility evaluation.

### **3.11 Changes to Preregistration**

In December 2022, updates relevant to the present protocol were made to the clinicaltrials.gov protocol (identifier: NCT04154631). These updates can be summarized as follows. First, minor changes were made to four inclusion and exclusion criteria, based on feasibility and preferred practices of CMHC partners. For instance, as described above, CMHCs preferred to determine which providers were eligible to deliver TranS-C, and thus, providers held a wider range of positions than we had originally anticipated. Additionally, in rare cases, providers outside of CMHCs participated in the study (e.g., a supervisee from a CMHC provider's private practice participated). Thus, we changed the provider criteria to be more inclusive (see provider inclusion criterion 1 above). Second, as the study unfolded, rich data emerged. To maximize the resources invested in this study, we decided to systematically capture these data with additional measures, now included in the 'Other Measures' section of clinicaltrials.gov. For example, the number of sessions delivered to each enrolled patient per provider was already being logged by the

facilitators. These data will be included in the dropout calculations and sensitivity analyses of the Implementation Phase main aims (see Measures and Planned Analyses). Third, as described above, to maximize recruitment goals, additional CMHC sites were recruited from new counties on an ongoing basis. We have added these additional sites/counties to clinicaltrials.gov. Fourth, the sample size has been changed to match the power analysis described above. The sample size in the original clinicaltrials.gov preregistration reflected a request from one reviewer of the National Institute of Mental Health grant to increase the sample size to account for a higher rate of dropout. However, this was deemed to be unfeasible, and the recruitment goal was adjusted to reflect the power analysis. Fifth, the type of design was corrected to be hybrid type 2, given the equal emphasis on determining effectiveness of an intervention (i.e., TranS-C) and feasibility/impact of an implementation strategy (i.e., adapting interventions to fit context) [48, 49]. Sixth, after launching the study, we received requests to minimize burden for patients. In response, assessors began consenting patients during pre-treatment assessments. Thus, we now specify that assessors are blind to condition at post-treatment and 6FU.

